5.7.2 Collection of biomarkers biological samples

Biological samples (archived tumor samples and blood samples) will be collected only from patients who are eligible to start study treatment and will be analyzed for exploratory biomarkers to assess correlations with disease activity, effects of study drug, clinical outcomes and toxicity:

- Mandatory: Archival tumor sample or fresh tumor biopsy
 - FFPE tumor sample from the primary or recurrent cancer must be available for central testing (or approximately 20 unstained sections mounted on glass slides prepared from the block). If there is not written confirmation of the availability of an archival tumor sample prior to enrollment, or if the patient does not consent to donating a fresh tumor biopsy sample (if an archival sample is unavailable), the patient is not eligible for the study. The tumor samples will be collected and will be analyzed for somatic deleterious or suspected deleterious variants in *BRCA1* or *BRCA2* genes, and the following HRR-associated genes: *ATM*, *BRIPI*, *PALB2*, *RAD51C*, *BARD1*, *CDK12*, *CHEK1*, *CHEK2*, *FANCL*, *PPP2R2A*, *RAD51B*, *RAD51D*, and *RAD54L*, to assess correlations with disease activity, effects of study drug, clinical outcomes and toxicity.
- Mandatory: Blood sample for biomarker analysis

- Blood samples for PBMC testing (8 mL) and plasma biomarker testing (5 mL) will be collected from all patients at baseline; at Week 4; at Week 8 and at discontinuation of IPs, for exploratory biomarker work.
- Blood sample (10 mL) at baseline and at discontinuation of IPs to evaluate ctDNA.

5.7.3 Storage, re-use and destruction of biological samples

Samples will be stored for a maximum of 15 years from the date of LSLV (ie, approximately 12 months after the last patient received her first dose of IP) after which they will be destroyed. The results of this biomarker research will be reported either in the CSR itself or as an addendum, or separately in a scientific report or publication. The results of this biomarker research may be pooled with biomarker data from other studies with the study drug to generate hypotheses to be tested in future research.

5.7.4 Labelling and shipment of biological samples

The Investigator ensures that samples are labelled and shipped in accordance with the Laboratory Manual and the Biological Substance, Category B Regulations (materials containing or suspected to contain infectious substances that do not meet Category A criteria), see Appendix C ‘IATA 6.2 Guidance Document’.

Any samples identified as Infectious Category A materials are not shipped and no further samples will be taken from the patient unless agreed with AstraZeneca and appropriate labelling, shipment and containment provisions are approved.

5.7.5 Chain of custody of biological samples

A full chain of custody is maintained for all samples throughout their lifecycle.

The Investigator at each center keeps full traceability of collected biological samples from the patients while in storage at the center until shipment or disposal (where appropriate).

The sample receiver keeps full traceability of the samples while in storage and during use until used or disposed of or until further shipment and keeps documentation of receipt of arrival.

AstraZeneca keeps oversight of the entire life cycle through internal procedures, monitoring of study sites and auditing of external laboratory providers.

Samples retained for further use are registered in the AstraZeneca Biobank system during the entire life cycle.

5.7.6 Withdrawal of Informed Consent for donated biological samples

If a patient withdraws consent to the use of donated biological samples, the samples will be disposed of/destroyed, and the action documented. If samples are already analyzed, AstraZeneca is not obliged to destroy the results of this research.

If the patient withdraws consent for the collection of the mandatory biological samples that are an integral part of the study (ie, the archival tumor sample or the mandatory biomarker blood samples), further study participation can be continued, if the patient is already receiving treatment with IPs.

The PI:

- Ensures patients' withdrawal of informed consent to the use of donated samples is notified immediately to AstraZeneca
- Ensures that biological samples from that patient, if stored at the study site, are immediately identified, disposed of /destroyed, and the action documented
- Ensures the laboratory(ies) holding the samples is/are informed about the withdrawn consent immediately and that samples are disposed of/destroyed, the action documented and the signed document returned to the study site
- Ensures that the patient and AstraZeneca are informed about the sample disposal.

AstraZeneca ensures the central laboratory(ies) holding the samples is/are informed about the withdrawn consent immediately and that samples are disposed of/destroyed and the action documented and returned to the study site.

5.8 Biological sampling procedures

5.8.1 Volume of blood

The volume of blood that will be drawn from each patient will vary, dependent upon the length of time that the patient remains in the trial. However, the volume of blood to be drawn from each patient (including for PK samples) during screening and up to and including Week 8 should not exceed 154 mL, according to National Institutes of Health (NIH) guidance ([NIH guidance 2009](#)).

The total volume of blood to be drawn from each patient in the study, assuming they complete screening, 48 weeks of treatment, a treatment discontinuation visit and the 30-day follow-up visit, should not exceed 335 mL.

The procedures for the collection, handling, and shipping of laboratory samples are specified in the Sample Handling and Logistics Manual supplied to sites.

Safety laboratory assessments will be performed locally by means of their established methods. The number of samples/blood volumes is therefore subject to site-specific change.

Extra blood samples may also be collected if, for example, additional samples are required for repeat safety assessments.

Drug: Study: Pembrolizumab (AZD2171) plus olaparib (AZD2281)
Study Code D8488C00001
Edition Number 5.0
Date 15 Jan 2019

The estimated total volume of blood that will be drawn from each patient in this study is as shown in [Table 6](#).

Table 6 Estimated maximum volume of blood to be drawn from each patient

Assessment	Sample volume (mL)	No. of samples - Screening	No. of samples Day 1 to Week 8	Every 4 weeks (Week 8 to treatments discontinuation)	Treatments Discontinuation visit	30 day follow-up visit	Final Protocol Visit
Whole Blood sample:	9	1					

 Prospective Myriad BRAC Analysis CDx® test for patients with unknown BRCA status or potential retrospective analysis in patients with a local test result 							
Blood sample for ctDNA	10	1			1		
Blood samples (PBMC) for biomarker analysis	8	1	2		1		
Blood samples (plasma) for biomarker analysis	6	1	2		1		
Safety Clinical chemistry (locally assessed)	5	1	5	1	1	1	1
Hematology (locally assessed)	5	1	5	1	1	1	1
Blood sample for CA-125 (locally assessed)	2	1	1	1	1	1	
Pharmacokinetic (Blood samples processed to plasma & frozen)	2 mL for cediranib + 2 mL for olaparib	0	8				
Total volume (mL)		55	112	12	36	12	10

Abbreviations: *BRCA* breast cancer susceptibility gene; CA-125 cancer antigen-125; ctDNA circulating tumor deoxyribonucleic acid; PBMC Peripheral blood mononuclear cell; PK Pharmacokinetics.

6. SAFETY REPORTING AND MEDICAL MANAGEMENT

The PI is responsible for ensuring that all staff involved in the study are familiar with the content of this section.

6.1 Definition of adverse events

An adverse event is the development of an undesirable medical condition or the deterioration of a pre-existing medical condition following or during exposure to a pharmaceutical product, whether or not considered causally related to the product. An undesirable medical condition can be symptoms (eg, nausea, chest pain), signs (eg, tachycardia, enlarged liver) or the abnormal results of an investigation (eg, laboratory findings, ECG). In clinical studies, an AE can include an undesirable medical condition occurring at any time, including run-in or washout periods, even if no IPs have been administered.

The term AE is used to include both serious and non-serious AEs.

6.1.1 Adverse Events of Special Interest

Adverse events of special interest (AESIs) are events of scientific and medical interest specific to the further understanding of the safety profiles of cediranib and olaparib; AESIs require close monitoring and rapid communication by the investigators to AstraZeneca. An AESI may be serious or non-serious.

- AESIs for cediranib are the Important Identified Risks: PRES, arterial thromboembolic events, and the Important Potential Risks: symptomatic left ventricular dysfunction and cardiac failure; nephrotic syndrome; renal thrombotic microangiopathy and liver failure.
- AESIs for olaparib are the Important Potential Risks of MDS/AML, new primary malignancy (other than MDS/AML) and pneumonitis.

6.2 Definitions of serious adverse event

An SAE is an AE occurring during any study phase that fulfils one or more of the following criteria:

- Results in death (NOTE: death is an outcome, not an event)
- Is immediately life-threatening (NOTE: the term “Life-Threatening” refers to an event in which the patient was at immediate risk of death at the time of the event; it does not refer to an event which could hypothetically have caused a death had it been more severe)
- Requires in-patient hospitalization or prolongation of existing hospitalization

- Results in persistent or significant disability/incapacity or substantial disruption of the ability to conduct normal life functions
- Is a congenital abnormality or birth defect
- Is an important medical event that may jeopardize the patient or may require medical intervention to prevent one of the outcomes listed above.

For further guidance on the definition of a SAE, see Appendix B to the Clinical Study Protocol. The full requirements of the ICH Guideline for Clinical Safety Data Management, Definitions and Standards for Expedited Reporting, Topic E2 will be adhered to.

6.3 Recording of adverse events

6.3.1 Time period for collection of adverse events

SAEs will be collected from time of signature of informed consent throughout the treatment period up to and including the 30-day follow-up period. AEs will be collected between the date of the first dose of IPs and the end of the 30-day follow-up period. All ongoing and any new AEs/SAEs identified during the 30 calendar days follow up period, after the last dose of IPs must be followed to resolution, unless resolution is unlikely to occur.

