- f. Patients should be closely monitored for adverse events which should be recorded, as they occur. SAEs that occurred during screening period will also be recorded. Patient diary data (via handheld electronic device) for blood pressure and diarrhea will be reviewed by the Investigator at each patient visit and any AEs and/or SAEs recorded in the AE eCRF
- g. All concomitant treatments will be recorded while the subject is taking IPs, together with the indication for which they are used
- h. Repeat assessment not required on Day 1, if already performed during previous 7 days for screening purposes
- i. Pulse rate, systolic and diastolic blood pressure, respiration rate, pulse oxygen saturation and temperature. Blood pressure should also be measured at the clinic weekly during the first 4 weeks of treatment, and every 2 weeks from Week 4 to Week 8 and every 4 weeks thereafter. Daily home blood pressure monitoring is required via patient self-monitoring. Patients are required to check their blood pressure twice daily for at least the first 8 weeks after starting study treatment, or, if antihypertensive management is required, until a stable anti-hypertensive regimen has been established, even if this requires more than 8 weeks. After 8 weeks or once a stable regimen has been achieved, blood pressure monitoring may be reduced to once daily. Daily blood pressure monitoring is required for as long as the patient remains on cediranib treatment and for 30 days after cediranib discontinuation, or until the FPV. Daily blood pressure monitoring by the patient will be recorded using a handheld electronic device See Section 5.2.4.1.
- j. Required at baseline, at every 8 weeks, until treatment discontinuation and at the 30-day safety follow-up visit, or until the FPV.
- k. ECGs are required within 7 days prior to starting IPs, and when clinically indicated thereafter. Any clinically significant changes on all other visits should be recorded as adverse events.
- l. Required for women of childbearing potential within 7 days prior to the start of IPs, every 4 weeks thereafter during study treatment. Pregnancy test for women of childbearing potential is required at the FPV and every 4 weeks thereafter until treatment discontinuation.

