6.3.4 Variables

The following variables will be collected for each AE;

- AE verbatim
- The date when the AE started and stopped
- Changes in CTCAE grade will be reported for AEs of diarrhea, fatigue, hypertension and nausea. For all other AEs, only the highest attained CTCAE grade will be reported.
- Whether the AE is serious or not
- Investigator causality assessment against each of the IP(s) (yes or no)
- Action taken with regard to each of the IP(s)
- Outcome (if resolved with sequelae then sequelae should be recorded).

In addition, the following variables will also be collected for SAEs:

- Date AE met criteria for SAE
- Date Investigator became aware of SAE
- AE seriousness criteria (see Section 6.2)
- If the patient was hospitalized:
 - Date of hospitalization
 - Date of discharge

The following variables will also be collected for deaths:

- Probable cause of death
- Date of death
- Autopsy performed
- Causality assessment in relation to IPs and/or Study procedure(s).

Investigators are also required to complete targeted safety questionnaires should any of the following events be reported: MDS/AML, new primary malignancy or pneumonitis.

The grading scales found in the NCI CTCAE version 4.03 will be utilized for all events with an assigned CTCAE grading. For those events without assigned CTCAE grades the recommendation is that the CTCAE criteria that convert mild, moderate and severe events into CTCAE grades should be used.

A copy of NCI CTCAE version 4.03 is available at http://evs.nci.nih.gov/ftp1/CTCAE/CTCAE_4.03_2010-06-14_QuickReference_8.5x11.pdf.

Adverse events not listed by CTCAE version 4.03 will be graded using the following criteria:

Intensity rating scale:

- 1 mild (awareness of sign or symptom, but easily tolerated)
- 2 moderate (discomfort sufficient to cause interference with normal activities)
- 3 severe (incapacitating, with inability to perform normal activities)

Alternative intensity rating scale for in-patients:

- 4 mild (awareness of sign or symptom, but easily tolerated)
- 5 moderate (disturbing but still tolerable)
- 6 severe (intolerable).

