Patients who are taking warfarin may participate in this trial; however, it is recommended that prothrombin time (International Normalized Ratio [INR] and activated partial thromboplastin time) be monitored carefully at least once per week for the first month, then monthly if the INR is stable. Subcutaneous heparin and low molecular weight heparin are permitted.

Anti-emetics/Anti-diarrheal

From screening onwards, should a patient develop nausea, vomiting and / or diarrhea, then these symptoms should be reported as AEs (see Section 6.3) and appropriate treatment of the event given.

Palliative radiotherapy

Palliative RT may be used for the treatment of pain at the site of bony metastases that were present at baseline, provided the investigator does not feel that these are indicative of clinical disease progression during the study period. Both IPs should be discontinued for a minimum of 3 days before a patient undergoes therapeutic palliative radiation treatment. Both IPs should be restarted within 4 weeks as long as any bone marrow toxicity has recovered.

Administration of other anti-cancer agents

Patients must not receive any other concurrent anti-cancer therapy, including investigational agents, while on one or both IPs. Patients may continue the use of bisphosphonates or denosumab for bone disease and corticosteroids for the symptomatic control of brain metastases provided the dose is stable before and during the study and they were started at least 4 weeks prior to the first doses of IPs.

Subsequent therapies for cancer

Details of first and subsequent therapies for cancer and/or details of surgery for the treatment of the cancer, after discontinuation of treatment, will be collected until the end of the study.

Other concomitant treatment

Other medication other than that described above, which is considered necessary for the patient's safety and well-being, may be given at the discretion of the Investigator and recorded in the appropriate sections of the eCRF.

In addition, any unplanned diagnostic, therapeutic or surgical procedure performed during the study period must be recorded in the eCRF.

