
8.4.3 Other endpoints

Patient reporting of CTCAE symptoms

The PRO-CTCAE questionnaire will be used to derive patient reporting of CTCAE symptoms: nausea, vomiting, diarrhea, decreased appetite, fatigue, and dizziness.

Safety variables

Safety and tolerability will be assessed in terms of AEs, deaths, laboratory data, vital signs including BP and ECGs. Any AE occurring before the start of IP will not be included in the summary tables of AEs.

Any AE occurring within 30 days of discontinuation of IPs (ie, the last dose of cediranib + olaparib) or the last dose of the last IP to be discontinued, in the rare case where discontinuation dates are different will be included in the AE summaries.

Blood pressure data collected electronically (see Section 5.2.4.1) will not be reported in the CSR. Patient profiles and BP data over time for patients may be evaluated in an exploratory analysis at a later time.

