3.3.3 AEs

AEs and SAEs will be collected throughout the study, from date of first dose of either IP until 30 days after the last dose of study medication. The Medical Dictionary for Regulatory Activities (MedDRA)(using the latest MedDRA version available at database lock) will be used to code the AEs. AEs will be graded according to the National Cancer Institute Common Terminology Criteria for AEs (CTCAE Version 4.03).

If partial dates of onset occur, a conservative approach will be followed and events will be assumed to be treatment emergent unless there is convincing evidence to the contrary.

The following variables will be collected for each AE;

- AE verbatim
- The date when the AE started and stopped
- Changes in CTCAE grade will be reported for AEs of diarrhoea, fatigue, hypertension and nausea. For all other AEs, only the highest attained CTCAE grade will be reported.
- Whether the AE is serious or not
- Investigator causality assessment against each of the IP(s) (yes or no)
- Action taken with regard to each of the IP(s)
- Outcome (if resolved with sequelae then sequelae should be recorded).

In addition, the following variables will also be collected for SAEs:

- Date AE met criteria for SAE
- Date Investigator became aware of SAE
- AE seriousness criteria
- If the patient was hospitalized:
- Date of hospitalization
- Date of discharge

The following variables will also be collected for deaths:

- Probable cause of death
- Date of death
- Autopsy performed
- Causality assessment in relation to IPs and/or Study procedure(s).

Groups of preferred terms will be used to identify adverse events of special interests (AESIs); these preferred terms will be listed before database lock and documented in the Study Master File. The AESIs for cediranib will include PRES, arterial thromboembolic events, symptomatic left ventricular dysfunction and cardiac failure, nephrotic syndrome, renal thrombotic microangiopathy, liver failure, diarrhea, fatigue, hypertension and nausea. The AESIs for olaparib will include MDS/AML, new primary malignancy (other than MDS/AML) and pneumonitis.

For the purposes of this study all AESIs identified above will be reported for both IPs.

Any AE occurring before the start of IP or more than 30 days after discontinuation of IPs will be included in the data listings but will not be included in the summary tables of AEs.

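### Protocol 6.3.1 and 7.7 start AE recording for nausea, vomiting and diarrhea at different times, and no rule says how a pre-dose AE that worsens on treatment is tabulated

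*Protocol*

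**What the plan says.** - **Start of collection.** Protocol 6.3.1: "AEs will be collected between the date of the first dose of IPs and the end of the 30-day follow-up period". For serious events the window opens earlier: "SAEs will be collected from time of signature of informed consent throughout the treatment period". Footnote f to Table 5 agrees, naming only serious events for screening: "SAEs that occurred during screening period will also be recorded".
- **Three symptoms treated differently.** Protocol 7.7, in its paragraph on anti-emetics and anti-diarrheals, refers back to section 6.3 but says: "From screening onwards, should a patient develop nausea, vomiting and / or diarrhea, then these symptoms should be reported as AEs".
- **Entry to the tables.** Protocol 8.4.3: "Any AE occurring before the start of IP will not be included in the summary tables of AEs". SAP 3.3.3: "Any AE occurring before the start of IP or more than 30 days after discontinuation of IPs will be included in the data listings", but kept out of the summary tables. SAP 4.2.9 repeats this and adds that such events are flagged in the listings.
- **Grades.** Protocol 6.3.4: "Changes in CTCAE grade will be reported for AEs of diarrhea, fatigue, hypertension and nausea". For every other AE, vomiting included, only the highest grade is kept. SAP 3.3.3 has the same rule.
- **Definition.** Protocol 6.1 counts as an AE "the deterioration of a pre-existing medical condition following or during exposure to a pharmaceutical product". It also allows an AE to occur before any study drug has been given.
- **Treatment emergence.** In deciding which AEs are tabulated, the SAP uses this idea only in its convention for partial onset dates (3.3.3), and does not define it.

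**The concern.** Two sections give sites different instructions for the same three symptoms. Both can be followed in good faith, and they produce different records. A site that follows 7.7 can open an AE with an onset date before first dose. The table rules then remove AEs that occur before dosing, and nothing says what happens if such an AE worsens on treatment.

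The SAP gives diarrhea and nausea special attention: it lists both among its AEs of special interest, with life tables, prevalence plots and grade-over-time plots. In a single-arm study the AE tables are the main account of tolerability. Whether a patient's worsening appears in them should not depend on which section the site read, or on how it chose to record a change in grade.

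**Working it through.** There is no stated figure to reproduce. The check traces one patient through the rules.

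**Case.** A patient develops grade 1 nausea, vomiting or diarrhea during screening. It does not resolve, and it reaches grade 3 after first dose.

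| Site practice | Record created | Result under 8.4.3, SAP 3.3.3 and 4.2.9 |
|---|---|---|
| Follows 6.3.1 | No AE at screening; the worsening is entered with a post-dose onset | Tabulated |
| Follows 7.7 and enters the deterioration as a new AE (consistent with 6.1) | A pre-dose AE and a second, post-dose AE | First listed only; second tabulated |
| Follows 7.7 and keeps one record | One AE with a pre-dose onset, carrying the later grade | Can be listed only, and so missing from the incidence, grade 3 or higher and related-AE tables |

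The third row assumes that an AE is taken to occur on its onset date. The documents do not say otherwise.

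**Could programming recover the third row?**
- *Diarrhea and nausea.* Grade changes are held within the AE, and SAP 4.2.9 plots them over time, so a post-dose increase could be identified. No rule asks for this when the tables are built.
- *Vomiting.* Only the highest grade is held. The variables listed in 6.3.4 include start and stop dates but not the date the highest grade was reached. A single record therefore cannot show whether the peak came before or after first dose.

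**Size per patient.** The planned sample is about 60 patients (protocol 8.2), and the safety set is everyone dosed. One patient lost from a term changes its incidence by 1/60 = 0.0167, or 1.7 percentage points. SAP 4.2.9 counts a patient once per preferred term. She therefore disappears from that term only if she has no other post-dose record under it. If she has one, the incidence is right but the maximum grade may be too low.

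**Direction.** The exclusion only removes records, so for affected patients the reported count or grade can fall but not rise.

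**Number of patients.** This would need three rates: how many develop one of these symptoms in screening and have it reported as an AE, in how many of them it continues and worsens on treatment, and how often the site keeps one record. The documents give none of the three.

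**The case against.** The strongest reply is that no passage excludes on-treatment worsening. Section 6.1 makes deterioration during exposure an AE in its own right, and the exclusions cover only AEs that occur before dosing. Section 6.3.4 does not say whether worsening across first dose stays in the old record or opens a new one. Section 5 leaves recording to the eCRF completion guidelines, which are not part of the documents and may settle it. This stands, and it is why the point is that worsening can be missed. It does not remove the gap. Neither the protocol nor the SAP tells sites to open a new record for these symptoms, and recording grade changes within an AE makes a single record a natural choice.

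The second reply is that few patients would be affected. Section 7.7 concerns symptoms that develop from screening onwards. Unresolved earlier toxicity goes into medical history (Table 5, footnote d), and exclusion criterion 12 removes most patients with persisting grade 2 or higher toxicity from earlier anti-cancer treatment. The screening window is at most 28 days. Section 6.8.4.3 describes nausea and vomiting on olaparib as intermittent, and a recurrence after resolution would be a new event. This also stands. It limits the likely number but does not make it zero.

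The third reply is that the signal remains visible elsewhere. Pre-dose AEs stay in the listings, grade-over-time plots are made for diarrhea and nausea, PRO-CTCAE covers all three symptoms from baseline, and QLQ-C30 has nausea/vomiting and diarrhea scales. This is true in part. None of these sources gives the investigator-graded incidence, grade 3 or higher or causally related counts, and there is no grade plot for vomiting.

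**Conclusion.** The conflict between 6.3.1 (with footnote f) and 7.7 is plain on the page, and no rule covers a pre-dose AE that worsens on treatment. Together they mean that such worsening can be left out of the AE tables at one site and counted at another. Each patient lost from a term is 1.7 points at N = 60, and the error runs only towards lower reported toxicity. The primary endpoint is not touched. The conclusion rests on two assumptions: that at least some sites follow 7.7 and keep one record, and that the tables classify an AE by its onset date.

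Two stronger readings are not supported.

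- A reader might infer that the plan discards all on-treatment worsening of these symptoms. It does not: under 6.1 the deterioration is an AE, and if entered as a new event it is tabulated.
- A reader might also put a total on the loss. Assuming that 5% to 30% of patients have symptoms at screening and that 25% to 75% of those worsen gives 60 x 0.05 x 0.25 = 0.75 to 60 x 0.30 x 0.75 = 13.5 patients. Neither range comes from the documents. The sum pools three symptoms that are tabulated separately, and it takes every site to follow 7.7 with a single record. The number affected cannot be estimated from the documents.

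**What to change.** 1. Reconcile protocol 6.3.1, Table 5 with its footnote f, and 7.7 to one start of collection. SAP 3.3.3 should be aligned at the same time, since it starts serious events at first dose whereas 6.3.1 starts them at consent.
2. State that symptoms present before first dose are recorded with their baseline grade, and that any worsening on or after first dose is entered as a new AE with its own onset date. Section 6.8.3.1 already records a baseline grade in medical history for hypertension. The new-record rule is needed for vomiting and for every other AE where only the highest grade is kept, because a grade increase cannot be programmed from one such record.
3. In protocol 8.4.3 and SAP 3.3.3 and 4.2.9, replace the exclusion with a treatment-emergent definition: onset on or after first dose, or onset before first dose with a grade increase on or after first dose, up to 30 days after last dose.

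The cost is a few sentences in the protocol and SAP, a line in the eCRF guidance and a change to the AE selection in the programs. For single vomiting records already collected with a pre-dose onset, sites would have to be asked when the highest grade was reached. Reported AE rates may come out slightly less favourable.
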